### 3.2.4. Cumulative Radiation Dosimetry for [F]FLT/CT + [F]Fluciclovine/CT

The dosimetry (mGy/10.0 mCi) for each radiotracer is summarized in Table 2. The proximate maximum administered activity for each tracer will be as follows: 10.0 mCi [F]FLT and 10 mCi [F]Fluciclovine. There is a maximum total of 6 PET/CT scans possible on this study. This includes baseline [F]FLT/CT and [F]Fluciclovine/CT, immediate post therapy [F]FLT/CT and [F]Fluciclovine/CT, and [F]FLT/CT and [F]Fluciclovine/CT at the time of pseudo-progression. A group of patients may only receive the [F]FLT/CT and [F]Fluciclovine/CT at the time of pseudo-progression. A low-dose CT is used for attenuation correction and will be obtained for each PET study.

Table 2. Cumulative Radiation Dosimetry

IRB #104740	[F]Fluciclovine -PET	[F]FLT-PET	Low Dose Head CT	PET/CT Total
Activity (mCi)	10	10	-	-
Number of Scans:	3	3	6	
Organ	Single Scan Absorbed dose (mGy)	Single Scan Absorbed dose(mGy)	Single Scan Absorbed dose(mGy)	Protocol Absorbed dose (mGy)
Adrenals	5.99	5.92	0.000367	35.74
Bladder	9.32	8.51	0.000009	53.50
Bone surfaces	8.58	7.03	0.626846	50.60
Brain	3.22	3.03	2.377692	33.03
Breasts	5.07	3.03	0.001513	24.32
Gallbladder	6.18	6.66	0.000069	38.52
Stomach	5.18	4.44	0.000223	28.86
Small intestine	4.88	4.81	0.000013	29.08
Colon	4.70	4.44	0.000011	27.42
Heart	19.13	4.44	0.001441	70.72
Kidneys	5.07	15.91	0.000159	62.94
Liver	12.40	17.76	0.000360	90.47
Lungs	12.77	4.07	0.005260	50.54
Muscles	3.92	3.63	0.051156	22.95
Oesophagus	4.63	3.63	0.003603	24.77
Ovaries	4.92	4.44	0.000000	28.08
Pancreas	37.81	5.55	0.000245	130.09
Red marrow	9.14	9.62	0.151308	57.18
Skin	2.96	2.78	0.158513	18.16
Spleen	8.81	8.14	0.000346	50.84
Testes	6.44	3.26	0.000000	29.08
Thymus	4.63	3.63	0.003603	24.77
Thyroid	3.81	3.48	0.100872	22.47
Uterus	16.50	4.44	0.000009	62.83
Effective dose (mSv)	8.18	5.55	0.10	41.79

## 4. RATIONALE, GOALS AND OBJECTIVES

### 4.1. Clinical Rationale

The standard treatment approach for patients with high-grade primary brain tumors includes maximum feasible surgical resection, followed by 6 weeks of concurrent cranial irradiation, and daily low-dose temozolomide chemotherapy; followed by 12 cycles of high-dose temozolomide administered for 5 consecutive days every 4 weeks (Stupp et al., 2005). Contrast-enhanced MRI is the current standard for evaluating the success of therapy and monitoring for tumor recurrence. MRI is typically obtained prior to initial surgery, within 24 hours after surgery, at the conclusions of cranial irradiation, and then every 8 weeks during temozolomide chemotherapy until evidence of recurrence. Despite this careful clinical and radiographic surveillance, and despite decades of research into the histologic and molecular classification of primary brain tumors, our ability to predict tumor behavior remains very limited. Some gliomas will result in overall survival times of only months, whereas other histologically-identical gliomas may yield survivals of years to decades (Curran et al., 1993, Carson et al., 2007). Current assessment of tumor response to therapy is also poor. Patients with complete radiographic response after cranial irradiation often progress rapidly post-irradiation. In contrast, some patients with enhancing masses at the end of chemoradiotherapy may respond dramatically to further chemotherapy alone; or the masses may even disappear in the absence of further therapy, so called “tumor pseudoprogression” (Chamberlain et al., 2007). This confounding situation demonstrates a need for better assessment of tumor response.

Improvements in the ability to predict tumor behavior prior to the start of therapy would allow more efficient and effective tumor surveillance; better prognostication; and more appropriate assignment of patients to conventional, aggressive, or investigational therapies early in their clinical courses. This would provide huge economic and social benefits, and could afford decisive insights into brain tumor physiology and biology. Similarly, the ability to identify, earlier and more accurately, whether individual patients were responding to therapy would allow prompt discontinuation of ineffectual treatments and institution of potentially more effective therapies.

Previous efforts using imaging for such tasks have generally been limited to a single modality (e.g. MRI) and/or single-tracer (e.g. FDG-PET). However, there is a significant and growing body of evidence that complementary imaging of multiple aspects of tumor physiology (i.e. using multiple PET tracers) can provide greatly enhanced information over imaging with a single modality or tracer alone. In solid tumors, complex interactions exist between blood flow, metabolic activity, and oxygen status which affect metastatic and proliferative activity. Heterogeneous tumors may contain both slow-growing and fast-growing regions that present different profiles of proliferation rates and amino acid uptake.

### 4.2. Hypotheses

The hypothesis of this exploratory clinical trial in patients with high-grade a primary brain tumor who receive chemoradiation is that the PET imaging agents [F]Fluciclovine and/or [F]FLT will be a better predictor of tumor response than standard MRI based brain tumor response criteria. When used in conjunction, the two PET agents may be better able to predict tumor aggressiveness and thus overall survival than the use of individual-tracer PET biomarkers. This may eventually lead to improved assessment of response (including time to progression and overall survival) and differentiation of tumor recurrence/progression from treatment effect (pseudoprogression).

### 4.3. Exploratory Objectives

#### 4.3.1. Exploratory Objectives

The primary objective of the study is to show that a 25% reduction in SUVmax or SUVmean for each of the PET imaging tracers will be predictive of overall survival

#### Secondary Exploratory Objectives

- Assess the association between overall survival and change in each of the following quantitative markers for [F]Fluciclovine and [F]FLT: K1-k4, Knet and Ktrans, from baseline to post therapy.
- Assess the association between progression free survival and change in each of the following quantitative markers for [F]Fluciclovine and [F]FLT: K1-k4, Knet and Ktrans, from baseline to post therapy.
- Assess the ability of [F]FLT and/or [F]Fluciclovine alone or together to predict true progression from pseudoprogression in patients with this clinical dilemma.
- A 25% reduction in SUVmax or SUVmean for each of the PET imaging tracers will be more predictive of longer overall survival than the current MRI based response criteria.
- A 25% reduction in SUVmax or SUVmean for each of the PET imaging tracers will be more predictive of time to progression than the current MRI based response criteria.

Two different groups of patients will be able to enroll in the trial. The first group, Group A, will be for patients who have not yet received any therapy for their suspected or newly found brain tumors. Group B will enroll patients with pathologically proven malignant brain tumor (WHO Grade III or IV glial-based tumors) who have undergone chemoradiation and have a contrast enhancing mass  $\geq 1.0$  cm in greatest diameter concerning for pseudoprogression. MRI-documented possible recurrence/progression versus treatment effect (pseudoprogression) within 6 months from the time of completion of chemoradiation.

Group A will have three different patient cohorts. The first, for patients where there is compelling evidence, based on the MRI and/or CT imaging, that a high-grade primary brain tumor is present. Pathologic confirmation will occur with subsequent biopsy or surgery. The second cohort of patients are individuals where the tumor is felt to be inoperable and a biopsy is performed but no surgery. The third cohort of patients are post-surgery where a complete surgical resection was not possible. This will be confirmed by a post-operative contrast MRI/CT scan where residual tumor  $\geq 1.0$  cm in diameter is present.

A number of quantitative and semi-quantitative imaging biomarkers for each tracer will be computed at each imaging time point, and the change in each biomarker between time-points will also be computed. These data will be compared with changes in tracer uptake before and after therapy and used to determine the semi-quantitative change in [F]FLT and [F]Fluciclovine uptake which is consistent with response based on standard brain tumor response. In addition the imaging biomarkers will be used to determine if they are predictive endpoints (survival, time to progression), and with tumor biologic information (histology, WHO grade, vascularity, MIB-1, VEGF, EGFR, p53, IDH status) in cases when tumor tissue becomes available from standard care. These data will provide pilot information regarding the potential value of concurrent multiple PET biomarkers for predicting tumor behavior prior to the start of therapy, for improved prognostication, for more efficient and effective tumor surveillance, and/or for more appropriate assignment of patients to conventional, aggressive, or investigational therapies early in their clinical courses.

All patients will receive standard tumor-directed therapy and will be monitored with conventional imaging according to standard of care, which may include MRI and FDG-PET as described earlier. The [F]FLT or

[F]Fluciclovine PET research scans will *not* affect clinical decisions. A database of demographic, clinical, and molecular biologic information for each patient will be created. Tissue samples, when available from routine care, will undergo detailed histopathologic evaluations, with results prospectively and systematically recorded. All patients will be followed until the end of the trial (at least 12 months post last imaging assessment) for important clinical endpoints as listed in Table 3.

**Table 3. PET Imaging Biomarkers, Clinical and Biologic Information Database**

PET Imaging Biomarkers a	Clinical and Biologic Information
[  F]FLT (proliferation): SUV max , SUV mean , SUV FLT net , K FLT net	Age at diagnosis, performance status, tumor size and location, radiographic characteristics, extent of surgery, dates and types of therapy.
[  F]Fluciclovine amino acid uptake: SUV max , SUV mean , SUV FLUC , K FLUC net	Tumor histology and WHO grade, vascularity, MIB-1, VEGF, EGFR, p53, IDH status Clinical and radiographic response, concomitant medications; time to progression, overall survival

a Quantitative and semi-quantitative imaging biomarkers

The data from multiple PET biomarkers combined with histologic and clinical data will enable identification and development of PET biomarker profiles which correlate with (and might be predictive of) tumor aggressiveness and clinical outcomes. The three imaging time point assessments serve multiple uses in this initial exploratory study. If baseline imaging can predict tumor aggressiveness and clinical outcomes, such imaging may potentially be used to guide selection of conventional, aggressive, or investigational therapies. The second time point, within 1-4 weeks after 6wks of chemoradiotherapy, will provide a measurement of tumor response that may potentially differentiate tumors that will progress rapidly from those that will not (changes in imaging biomarkers between exams 1 and 2 will likely be important for this determination). Finally, the multi-tracer array at the time of treatment effect (pseudoprogression) versus true recurrence/progression may yield new insights into the physiology and biology of these tumors, and multi-tracer imaging may help to differentiate recurrence from radiation necrosis/treatment effect (pseudoprogression). We believe the complementary value of the two tracers in conjunction has much greater potential for meeting these goals than any one tracer alone. For example, tumors with high proliferation ([F]FLT) and/or growth ([F]Fluciclovine) may respond best to anti-EGFR-directed agents or conventional cytotoxic chemotherapies. Of specific interest, is there a multi-tracer PET signature that distinguishes between treatment effect (pseudoprogression) and true progression/recurrence that will have important clinical utility? These questions will be studied in detail, developing formal hypotheses that will be tested in future phase II/III clinical trials.

## 5. TRIAL DESIGN

### 5.1. Patient Eligibility

Two different groups of patients will be able to enroll in the trial. The first group, Group A, will be for patients who have not yet received any therapy for their suspected or newly found brain tumors. Group B will enroll patients with pathologically proven malignant brain tumor (WHO Grade III or IV glial-based tumors) who have undergone chemoradiation and have a contrast enhancing mass ≥ 1.0 cm in greatest diameter concerning for pseudoprogression. MRI-documented possible recurrence/progression versus treatment effect (pseudoprogression) within 6 months from the time of completion of chemoradiation.

Group A will have three different patient cohorts. The first, for patients where there is compelling evidence, based on the MRI and/or CT imaging, that a high-grade primary brain tumor is present. Pathologic confirmation will occur with subsequent biopsy or surgery. The second cohort of patients are individuals where the tumor is felt to be inoperable and a biopsy is performed but no surgery. The third cohort of patients are post-surgery where a complete surgical resection was not possible. This will be confirmed by a post-operative contrast MRI/CT scan where residual tumor  $\geq 1.0$  cm in diameter is present.

Eight to ten patients per year will be enrolled, for a total of 30 patients. Providers within the Radiation Oncology and Neuro-Oncology departments will identify and recruit patients who may be eligible participants.

## 5.2. Inclusion Criteria

- Two adult patient groups will be eligible for inclusion in this study:
  - Group A: Patients where there is compelling evidence, based on the MRI and/or CT imaging, that a high-grade primary brain tumor is present. Pathologic confirmation will occur with biopsy or surgery.  
Patients whose tumor is felt to be inoperable and a biopsy is performed but no surgery.  
Patients with a newly diagnosed primary malignant brain tumor (WHO Grade III or IV) who will be receiving chemoradiation and who either did not undergo surgical resection or underwent incomplete resection with residual tumor  $\geq 1.0$  cm in greatest diameter by contrast MRI postoperatively.
  - Group B: Patients with pathologically proven malignant brain tumor (WHO Grade III or IV glial-based tumors) who have undergone chemoradiation and have MRI-documented possible recurrence/progression versus treatment effect (pseudoprogression) within 6 months from the time of completion of chemoradiation.
- Patients must be 18 years or older for inclusion in this study. There is little experience with the safety of [F]FLT or [F]Fluciclovine in children, and the risks associated with radiation exposure may be increased for children under 18 years old as well.
- Patients must document their willingness to be followed for up to 24 months after recruitment by signing informed consent documenting their agreement to have clinical endpoints and the results of histopathologic tissue analysis (when tissue becomes available from routine care) entered into a research database.
- All patients, or their legal guardians, must sign a written informed consent and HIPAA authorization in accordance with institutional guidelines.
- Determination of pregnancy status: Female patients who are not postmenopausal or surgically sterile will undergo a serum pregnancy test prior to each set of [F]FLT and [F]Fluciclovine PET scans. A negative test will be necessary for such patients to undergo research PET imaging.
- Pre-imaging laboratory tests must be performed within 28 days prior to the [F]FLT imaging procedure. These must be less than 4.0 times below or above the upper or lower limit range for the respective laboratory test for entry into the study (unless clinically not relevant). In those instances where a laboratory value is outside of this range, then such a patient will be ineligible for enrollment unless at the discretion of the PI the abnormal lab value is of no clinical significance to the safety or integrity of the study results. For follow-up scanning sessions after therapy has been instituted, laboratory testing will also be required due to the use of [F]FLT. The patients have brain tumors and will have received chemoradiation; therefore, many routine laboratory tests may not be within the typical normal range. As such, a factor of 4.0 times above or below the upper or lower value for the normal range for any laboratory test will also be used to determine the acceptable range for the

2nd and possibly 3rd imaging time points (unless clinically not relevant as explained above). The baseline laboratory testing will include liver enzymes (ALT, AST), bilirubin (total), serum electrolytes, CBC with platelets, prothrombin time, partial thromboplastin time, BUN, and creatinine. For those patients receiving coumadin or another anticoagulant the upper limit for prothrombin time or partial thromboplastin time must not exceed 6 times the upper limit of the normal range. (Appendix E, Laboratory Study Results).

### **5.3. Exclusion Criteria**

[figure not shown]
- Patients with known allergic or hypersensitivity reactions to previously administered radiopharmaceuticals. Patients with significant drug or other allergies or autoimmune diseases may be enrolled at the Investigator's discretion.
- Patients who are pregnant or lactating or who suspect they might be pregnant. Serum pregnancy tests will be obtained prior to each set of multi-tracer PET scans in female patients that are not postmenopausal or surgically sterile.
- Adult patients who require monitored anesthesia for PET scanning.
- Patients who are too claustrophobic to undergo PET scanning.
- Known HIV positive patients due to the previous toxicity noted with [F]FLT in this patient group.

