## APPENDIX A: Eligibility Check List

**Patient Name:** \_\_\_\_\_ **MRN:** \_\_\_\_\_

**Person Confirming Eligibility:** \_\_\_\_\_ **Date:** \_\_\_\_\_

\_\_\_\_\_ (Yes/No) Patient is  $\geq$  18 years old.

\_\_\_\_\_ (Yes/No) Group A. Either patients where there is compelling evidence, based on the MRI and/or CT imaging, that a high-grade primary brain tumor is present. Pathologic confirmation will occur with biopsy or surgery. OR patients whose tumor is felt to be inoperable and a biopsy is performed but no surgery. OR patients with a newly diagnosed primary malignant brain tumor (WHO Grade III or IV) who will be receiving chemoradiation and who either did not undergo surgical resection or underwent incomplete resection with residual tumor  $\geq$  1.0 cm in greatest diameter by contrast MRI postoperatively.

\_\_\_\_\_ (Yes/No) Group B. Patients with pathologically proven malignant brain tumor (WHO Grade III or IV glial based tumors) who have undergone chemoradiation and have MRI-documented (contrast enhancing mass  $\geq$  1.0 cm in greatest diameter) possible recurrence/progression versus treatment effect (pseudoprogession) within 6 months from the time of completion of chemoradiation.

\_\_\_\_\_ (Yes/No) Patient is willing to have their clinical records reviewed for at least 24 months after enrollment.

\_\_\_\_\_ (Yes/No) Patient, or their legal guardians, have signed a written informed consent and HIPAA authorization in accordance with institutional guidelines.

\_\_\_\_\_ (Yes/No) If patient is female, she must be postmenopausal for a minimum of one year, surgically sterile, or is willing to undergo a serum pregnancy test prior to each imaging session.

\_\_\_\_\_ (Yes/No) Patient is not lactating.

\_\_\_\_\_ (Yes/No) Pre- [F]Fluciclovine and [F]FLT PET laboratory tests not greater than 4.0 $\times$  the upper or lower values in the normal range: liver enzymes (AST, ALT, ALK), bilirubin (total), serum electrolytes, CBC with platelets, prothrombin time, partial thromboplastin time, BUN, and creatinine. For those patients receiving coumadin or another anticoagulant the upper limit for prothrombin time or partial thromboplastin time must not exceed 6 times the upper limit of the normal range.

\_\_\_\_\_ (Yes/No) Patient does not have allergic or hypersensitivity reactions to previously administered radiopharmaceuticals.

\_\_\_\_\_ (Yes/No) Patient does not require monitored anesthesia for PET/CT imaging.

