## APPENDIX B: Schedule of Events

	Screen	Imaging Session 1		Imaging Session 2		Imaging Session 3	
		[  F]FLT	[  F]Fluciclovine	[  F]FLT	[  F]Fluciclovine	[  F]FLT	[  F]Fluciclovine
Assessment/ Procedures							
Informed Consent	X						
Inclusion/ Exclusion Criteria	X						
Laboratory Monitoring	X 			X 		X 	
Infusion of [  F]FLT		X		X		X	
[  F]FLT PET/CT Imaging		X		X		X	
Infusion of [  F]Fluciclovine			X		X		X
[  F]Fluciclovine PET/CT Imaging			X		X		X
Vital Signs 		X 	X 	X 	X 	X 	X 
AE Assessment		X	X	X	X	X	X
Concomitant Medication		X 		X 		X 	

- Laboratory tests will include: (AST, ALT), bilirubin (total), serum electrolytes, CBC with platelets, prothrombin time, partial thromboplastin time, BUN, and creatinine. Female patients who are not postmenopausal or surgically sterile will undergo a serum pregnancy test prior to each imaging session ([F]FLT and [F]Fluciclovine PET scans). The values for the imaging sessions must be within 4.0 X the upper or lower normal limits (unless clinically not relevant). For those patients receiving coumadin or another anticoagulant the upper limit for prothrombin time or partial thromboplastin time must not exceed 6 times the upper limit of the normal range.
- Laboratory tests from the screening visit will be used if the first [F]FLT imaging session are performed within 28 days of the screening laboratory tests. Labs will be redrawn prior to [F]FLT imaging session 1 if they are outside of the 28 day window prior to the scan.
- Within 96 hours prior to the second [F]FLT imaging session the laboratory assessments will be performed. The values for this assessment must be within 4.0 X the upper or lower normal limits (unless clinically not relevant). For those patients receiving coumadin or another anticoagulant the upper limit for prothrombin time or partial thromboplastin time must not exceed 6 times the upper limit of the normal range.

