- Within 96 hours prior to the possible third [F]FLT imaging session the laboratory assessments will be performed. The values for this assessment must be within 4.0 X the upper or lower normal limits (unless clinically not relevant). For those patients receiving coumadin or another anticoagulant the upper limit for prothrombin time or partial thromboplastin time must not exceed 6 times the upper limit of the normal range.
- Includes: Heart Rate, Blood Pressure, and Temperature. Vitals signs will be collected prior to infusion and again at the completion of the imaging study. Height and weight will be recorded at the beginning of an imaging session.
- To be collected prior to the first imaging time point of each session, regardless of whether [F]FLT or [F]Fluciclovine is the first imaging to take place.
- For patients enrolling under Group B, laboratory tests from the screening visit will be used if they are performed within 28 days of the imaging session.

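### Sections 5.2 and 5.3 require a pregnancy test per two-tracer set, the appendices per imaging session, and the second injection can come 14 days or more after the test

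*Combined protocol and SAP*

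**What the plan says.** The rule appears in four places and uses two different units.

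- **Per set.** Section 5.3: "Serum pregnancy tests will be obtained prior to each set of multi-tracer PET scans". Section 5.2 also ties the test to each set of FLT and fluciclovine scans, and adds: "A negative test will be necessary for such patients to undergo research PET imaging".
- **Per imaging session.** The Appendix A checklist asks whether the patient "is willing to undergo a serum pregnancy test prior to each imaging session". Appendix B, footnote 1: "Female patients who are not postmenopausal or surgically sterile will undergo a serum pregnancy test prior to each imaging session". A parenthesis naming both tracer scans follows.

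The closing paragraph of Appendix B (Multi-Tracer PET Imaging Visit) puts the two tracers on separate days, with all imaging days inside one to two weeks. Footnote 6 allows either tracer to come first.

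The time windows in Appendix B are written for laboratory tests. Footnote 2 accepts screening results when the first FLT scans "are performed within 28 days of the screening laboratory tests". Footnotes 3 and 4 set the later windows: "Within 96 hours prior to the second" and "Within 96 hours prior to the possible third" FLT session. Footnote 7 gives Group B 28 days to the imaging session. In Section 5.2 the stated reason for follow-up bloods is FLT: "laboratory testing will also be required due to the use of" that tracer. None of these windows is expressly assigned to the pregnancy test, and none is tied to the fluciclovine injection as such.

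**The concern.** The protocol treats a negative test as necessary for scanning, and Section 3.1.4 regards fluciclovine as unsuitable in pregnancy. Both tracers expose the uterus: Table 2 gives 16.50 mGy per fluciclovine scan and 4.44 mGy per FLT scan. A test tied to the set protects the first injection. It says less about the second, because a conception after the blood draw, or one too recent to detect at that draw, would be missed.

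At stake is an avoidable fetal exposure in a woman whom the protocol means to exclude. The two units also leave sites unsure what is asked of them. A site working from Sections 5.2 and 5.3 and a site that reads Appendix B as meaning each scan would act differently, and each could say that it followed the protocol.

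**Working it through.** No power or significance calculation is involved. The check has two parts: what the wording means, and how old the test can be at the second injection.

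**Meaning of the unit**

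| Text | Unit it points to |
|---|---|
| Sections 5.2 and 5.3 | The pair: a set of FLT and fluciclovine scans |
| Appendix B column headings | The pair: each numbered session has an FLT and a fluciclovine column |
| Appendix B, footnote 6 | The pair: it speaks of the first imaging of a session, whichever tracer that is |
| Appendix B, footnotes 2 to 4 | A single scan: they speak of FLT imaging sessions |
| Appendix B, footnote 1, parenthesis | Either: it names both scans |
| Section 8.4.1 | Related usage: up to six scanning visits, one per injection |

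Sections 5.2 and 5.3 are clear. Appendices A and B can be read either way.

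**Age of the test under Sections 5.2 and 5.3**

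Input: the gap between injections is at most 2 weeks = 14 days (Appendix B).

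Age at second injection = age at first injection + gap.

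Best case, with blood drawn on the day of the first injection: 0 + 14 = **14 days**. This figure needs no assumption about windows. An earlier draw adds to it, and no limit is expressly stated.

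**Age if the laboratory windows are assumed to cover the pregnancy test** (96 hours = 4 days, 14-day gap)

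| Situation | Age at second injection |
|---|---|
| Group A sessions 2 and 3, FLT first | up to 4 + 14 = 18 days |
| Group A session 1, FLT first | up to 28 + 14 = 42 days |
| Group A session 1, fluciclovine first | up to 28 days; one test can serve, since 14 ≤ 28 |
| Group A sessions 2 and 3, fluciclovine first | at most 4 days; one test cannot serve, since 14 > 4, so a second is needed |
| Group B, either order | 28 + 14 = 42 days if the 28 days run to the first injection; 28 if to the second |

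**Number of tests**

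Three sets give 3 × 2 = 6 injections. One test per set gives 3 tests, so testing before every injection adds at most 6 − 3 = 3. The baseline of 3 is not fixed. With the windows applied, fluciclovine first and FLT more than 4 days later, the existing rules already need 1 + 2 + 2 = 5. If each scan counts as a session, they already need 6.

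**After the change**

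With a 96-hour window before each injection, the test is at most 4 days old at either injection, in either order.

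**The case against.** The strongest reply is that the appendices may already require a test before each tracer. Footnotes 2 to 4 use *imaging session* for one FLT scan, the parenthesis in footnote 1 names both scans, and Section 8.4.1 counts six visits. Footnote 5 has height and weight recorded at the start of a session, and the flow charts in Appendices C and D each have fields for them. This stands. A reader might infer that the protocol as a whole requires only one test for two injections; the documents do not support that. They support a clear per-set rule in the eligibility criteria and an ambiguous rule in the appendices, which may conflict with it.

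A reader might also take the 18- to 42-day figures as established, or count exactly three tests for six injections. Neither is secure. The longer ages require the laboratory windows to govern the pregnancy test. Footnote 1 of Appendix B does mention the test alongside the laboratory panel, but Section 5.2 puts it in a separate bullet and leaves it out of its list of baseline laboratory tests. The count changes with the reading and the tracer order, as shown above.

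Finally, safeguards exist and few women are concerned. Women who suspect pregnancy are excluded and a negative test is necessary. The first depends on suspicion and cannot pick up an unsuspected early pregnancy; the second does not say how recent the test must be. Small numbers limit how often the problem could arise, but not its seriousness if it did.

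**Conclusion.** The point holds as a patient-safety improvement that is worth making. Sections 5.2 and 5.3 tie the test to the set, the appendices use a term with two meanings, and nothing clearly requires a repeat before the second injection. A site that follows the eligibility sections as written can inject the second tracer on a negative test 14 days old, even with same-day testing before the first. That figure rests only on the two-week maximum gap. Anything longer is conditional, because no window is expressly assigned to the test.

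The number of women affected is probably small: Section 5.1 plans 30 patients in total, and the documents do not say how many could become pregnant. The primary endpoint, its analysis and the power are untouched.

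**What to change.** Use one rule in Section 5.2, Section 5.3, Appendix A and Appendix B: a negative serum pregnancy result within a short fixed window before each tracer injection, with FLT and fluciclovine both named. The sponsor and the IRB should set the window; 96 hours or less would match the one already used for follow-up laboratory tests. Let one test serve both tracers when both injections fall inside the window. Record the result and its date before each injection, on whichever study form the sponsor prefers; the flow charts in Appendices C and D show no field for it at present.

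The cost is wording in four places and usually one additional test per set, at most 3 over the study for a woman who completes all three sets. It applies only to women who are neither postmenopausal nor surgically sterile, and only when the two injections do not fit one window. Some existing tests may need re-timing. Because each tracer is made on the day of scanning, a late result carries a small risk of delaying or losing a dose.
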